### 7.2.3 End of long-term follow-up

*Section modified by Amendments 1 (Section 13.1) and 2 (Section 13.2.1.2, 13.2.1.4, and 13.2.1.9).*

The end of study assessments for subjects who are in this follow-up study will include the following:

- All radium-223 dichloride-/placebo-related AEs and related SAEs have to be documented and reported. Concomitant treatment associated with these events will not be collected unless it is cancer medication / treatment (including any systemic cytotoxic chemotherapy or radiotherapy for any malignancy; androgen synthesis inhibitors / androgen-receptor antagonists and radiation treatment; excluding analgesics). If a subject is unable to provide required details for events of interest, this information will need to be obtained from the primary provider.
- All occurrences of leukemia, myelodysplastic syndrome, aplastic anemia, primary bone cancer, or any other new primary malignancy must be reported as SAEs at any time and regardless of the investigator's causality assessment.
- All bone fractures and bone associated events (e.g., osteoporosis) should be collected as either AEs or SAEs if the criteria of SAE were met, regardless of the investigator's causality assessment.
- Cancer treatment (including any systemic cytotoxic chemotherapy or radiotherapy for any malignancy; androgen synthesis inhibitors / androgen-receptor antagonists and radiation treatment; excluding analgesics).
- Any BHA treatment taken during the study period must be recorded.
- In subjects who receive cytotoxic chemotherapy, all occurrences of febrile neutropenia or hemorrhage during chemotherapy treatment and for up to 6 months thereafter at a frequency based on local clinical practice.
- Survival status.

Subject data collected at other standard-of-care visits and / or contacts may be used to satisfy study-required data.

It is the clinical site's responsibility to obtain and make available the source documentation for the information collected from the subject and document it in the eCRF.

## 7.3 Population characteristics

This study will enroll subjects from selected company-sponsored feeder trials who received at least 1 dose of study drug (radium-223 dichloride or placebo).

### 7.3.1 Demographic

Demographic information will be carried over from the selected feeder trials.

### 7.3.2 Medical history

*Section modified by Amendment 1 (Section 13.1).*

All medical history will be carried over from the selected feeder trials.

## 7.4 Pharmacokinetics / pharmacodynamics

*Section modified by Amendments 1 (Section 13.1).*

No pharmacokinetic or pharmacodynamics assessments will be performed for this study.

## 7.5 Safety

*Section modified by Amendments 1 (Section 13.1) and 2 (Section 13.2.1.2 and 13.2.1.9).*

The investigator(s) and the sponsor's representative will review the safety data throughout the course of the study. The following safety variables will be evaluated:

- Adverse events: radium-223 dichloride-/placebo-related AEs and related SAEs will be collected and recorded on an ongoing basis throughout the study as described in Section 7.5.1.
- All occurrences of leukemia, myelodysplastic syndrome, aplastic anemia, primary bone cancer, or any other new primary malignancy.
- All bone fractures and bone associated events (e.g., osteoporosis), regardless of investigator assessment of causality
- In subjects who receive cytotoxic chemotherapy, all occurrences of febrile neutropenia or hemorrhage during chemotherapy treatment and for up to 6 months thereafter at a frequency based on local clinical practice.
- Deaths

### 7.5.1 Adverse events

#### 7.5.1.1 Definitions

*Section modified by Amendments 1 (Section 13.1) and 2 (Section 13.2.1.2).*

##### Definition of AE

In a clinical study, an AE is any untoward medical occurrence (i.e., any unfavorable and unintended sign [including abnormal laboratory findings], symptom or disease) in a patient or clinical investigation subject after providing written informed consent for participation in the study. Therefore, an AE may or may not be temporally or causally associated with the use of a medicinal (investigational) product.

In this study, for an event to be classified as an AE, it must be considered to be related to radium-223 dichloride/placebo by the investigator, and ongoing at or occurring from the time of the signing of the ICF and the end of the study. Also classified as AEs (regardless of the investigator's causality assessment) are all occurrences of leukemia, myelodysplastic syndrome, aplastic anemia, primary bone cancer, or any other new primary malignancy; all bone fractures and bone associated events (e.g., osteoporosis) regardless of the investigator's

causality assessment; and, in subjects who receive cytotoxic chemotherapy, all occurrences of febrile neutropenia or hemorrhage.

A surgical procedure that was planned prior to the start of the study by any physician treating the subject should not be recorded as an AE (however, the condition for which the surgery is required may be an AE).

In the following definitions of AEs from the feeder trials, the term “condition” may include abnormal symptoms and diseases.

- Conditions considered to be related to radium-223 dichloride/placebo by the investigator that started before signing of informed consent and for which symptoms or treatment are present after signing of informed consent will be carried over from the feeder trial and documented as AEs.
- Conditions considered to be related to radium-223 dichloride/placebo by the investigator that started or deteriorated after signing of informed consent will be documented as AEs. This includes intercurrent illnesses considered to be related to radium-223 dichloride/placebo by the investigator.

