### **3.2 Primary and secondary variables**

*Section modified by Amendments 1 (Section 13.1) and 2 (Section 13.2.1.2).*

This long-term follow-up study will enroll subjects who will be transferred from selected company-sponsored trials with radium-223 dichloride (feeder trials).

The primary variables are all safety-related and include:

- Incidence of and severity of radium-223 dichloride-/placebo-related AEs
- Incidence of radium-223 dichloride-/placebo-related SAEs
- Incidence of leukemia, myelodysplastic syndrome, aplastic anemia, and primary bone cancer or any other new primary malignancy
- Incidence of bone fractures and bone associated events (e.g., osteoporosis), regardless of investigator assessment of causality
- In subjects who receive cytotoxic chemotherapy: incidence of febrile neutropenia or hemorrhage during their chemotherapy treatment and for up to 6 months thereafter at a frequency based on local clinical practice

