## 6. Non-study therapy

### 6.1 Prior and concomitant therapy

*Section modified by Amendments 1 (Section 13.1) and 2 (Sections 13.2.1.3, 13.2.1.4, 13.2.1.5, and 13.2.1.7).*

Continuation or start of any background therapy and concomitant treatment including as part of a clinical trial is allowed in this follow-up study; however, continuation of feeder trial study drug is not allowed. Radium-223 dichloride should not be given concurrently with abiraterone plus prednisone/prednisolone.

All cancer treatments or medications (including any systemic cytotoxic chemotherapy or radiotherapy for any malignancy; androgen synthesis inhibitors / androgen-receptor antagonists and radiation treatment; excluding analgesics) received during this follow-up study will be recorded. The generic or trade name, indication, dosage, and start and stop dates must be recorded.

Based on the available data on radium-223 dichloride, the option of starting a BHA should be considered, taking into consideration applicable guidelines. Any BHA treatment taken during the study period must be recorded.

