### 7.2.2 Long-term follow-up

*Section modified by Amendments 1 (Section 13.1) and 2 (Section 13.2.1.2, 13.2.1.4, and 13.2.1.9).*

Subjects, their treating health care professional, or caregiver will be contacted by telephone (face-to-face data collection is possible and will replace the telephone contact if the subject is on-site within the time window of the planned telephone contact) every 6 months ( $\pm$  28 days) for 7 years (or follow-up as defined in the feeder trial protocols) following the last radium-223 dichloride or placebo treatment in the feeder trial or until death, to determine the following:

- All radium-223 dichloride-/placebo-related AEs and related SAEs occurring during this period have to be documented and reported. Concomitant treatment associated with these events will not be collected unless it is cancer medication / treatment (including any systemic cytotoxic chemotherapy or radiotherapy for any malignancy; androgen synthesis inhibitors / androgen-receptor antagonists and radiation treatment; excluding analgesics) or new BHA treatment. If a subject is unable to provide required details for events of interest, this information will need to be obtained from the primary provider.
- All occurrences of leukemia, myelodysplastic syndrome, aplastic anemia, primary bone cancer, or any other new primary malignancy must be reported as SAEs at any time and regardless of the investigator's causality assessment.
- All bone fractures and bone associated events (e.g., osteoporosis) should be collected as either AEs or SAEs if the criteria of SAE were met, regardless of the investigator's causality assessment.
- Cancer treatment (including any systemic cytotoxic chemotherapy or radiotherapy for any malignancy; androgen synthesis inhibitors / androgen-receptor antagonists and radiation treatment; excluding analgesics).
- Any BHA treatment taken during the study period must be recorded.
- In subjects who receive cytotoxic chemotherapy, all occurrences of febrile neutropenia or hemorrhage during chemotherapy treatment and for up to 6 months thereafter at a frequency based on local clinical practice.
- Survival status.

Training for conducting the follow-up contacts will be provided to clinical site personnel including, but not limited to, use of a telephone script. Subject data collected at other standard-of-care visits and / or contacts may be used to satisfy study-required data.

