Per protocol, febrile neutropenia and hemorrhage AEs are to be collected during and within 6 months of cytotoxic chemotherapy treatment. For the protocol-specified analysis of the incidence of febrile neutropenia or hemorrhage during their chemotherapy treatment and for up to 6 months thereafter, a simplified analysis will be performed, of febrile neutropenia and hemorrhage AEs without regard to cytotoxic chemotherapy association. All 16996-emergent febrile neutropenia and hemorrhage AEs documented in the study CRF will be reported, without regard to chemotherapy treatment.

For the analysis of fractures and bone associated events, separate analyses of patients with bone fractures, patients with bone associated events, and patients with bone fractures and/or bone associated events will be performed. The applicable MedDRA appendix will identify the MedDRA preferred terms applicable to each sub-category.

Unless otherwise specified, the analysis for each AE category will include a summary of the total number and percent of SAF-LTF participants with an AE of the applicable category. Participants with an applicable AE will be summarized by MedDRA preferred term (PT), overall within each applicable MedDRA system organ class (SOC), and overall (any applicable AE), both by worst CTCAE grade and for any grade. For summaries by worst grade, the AE with the worst grade in the applicable summary category will be used. AEs with missing grade will be included in any-grade summaries but not in summaries by worst grade. In addition, listings will be provided.

6.4.2.1 16996-Collected Adverse Events

All AEs collected in study 16996, whether or not collection was required per study 16996 protocol, will be listed for SAF-LTF including AE PT, 16996-emergent (Y/N), start and stop dates, grade, treatment-related (Y/N), serious (Y/N), reason for seriousness, outcome of AE, and time (days) since last dose of study drug. The listing will include all 16996-collected AEs, whether or not emerging within study 16996.

6.4.2.2 16996-Emergent Adverse Events

Summaries of the total number and percent of SAF-LTF participants with an AE of the following categories of 16996-emergent AEs will be presented:

• All 16996-emergent adverse events

Statistical Analysis Plan

Protocol No.: BAY 88-8223/16996

Page: 13 of 17

- Radium-223 dichloride- or placebo-related 16996-emergent AEs;
- Radium-223 dichloride- or placebo-related serious 16996-emergent AEs;

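### The AE definition omits the chemotherapy window for febrile neutropenia and hemorrhage, and the SAP has no step that restores it, so the primary variable is not reported as defined

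*Protocol*

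**What the plan says.** Protocol Section 3.2 makes this a primary variable, with a population (recipients of cytotoxic chemotherapy) and a time window: "incidence of febrile neutropenia or hemorrhage during their chemotherapy treatment and for up to 6 months thereafter". The objectives (Section 2), the design overview (3.1), Table 7-1 and the safety section (7.5) carry the same restriction. So do the visit sections 7.2.2 and 7.2.3, where the site is told to determine "all occurrences of febrile neutropenia or hemorrhage during chemotherapy treatment and for up to 6 months thereafter".

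Section 7.5.1.1, which tells the site what counts as an AE in this study, is the exception. It lists, among events that are AEs whatever the causality, "in subjects who receive cytotoxic chemotherapy, all occurrences of febrile neutropenia or hemorrhage", and stops there. The only time limits in that definition are general ones: "ongoing at or occurring from the time of the signing of the ICF and the end of the study".

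On the exposure side, Section 6.1 says that cancer treatments "received during this follow-up study will be recorded", and adds: "The generic or trade name, indication, dosage, and start and stop dates must be recorded".

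SAP Section 6.4.2 reads the collection rule as windowed, but then simplifies the analysis: "All 16996-emergent febrile neutropenia and hemorrhage AEs documented in the study CRF will be reported, without regard to chemotherapy treatment". The result is the number and percentage of SAF-LTF participants with such an event. SAP Section 7.2 declares this as a departure from the protocol's planned analysis.

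**The concern.** Two rules in one protocol govern collection for the same primary variable. A site working from the AE definition would record a hemorrhage years before or after a chemotherapy course. A site working from the visit sections would not, unless it judged the event related to radium-223 or placebo.

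That would be harmless if the analysis applied the window. It does not: whatever is in the CRF and arose or worsened after consent is counted, over a denominator that is not limited to chemotherapy recipients. The reported percentage can therefore move with the section a site followed, and with how long recipients are followed and survive. Protocol Section 3.3 expects the placebo subjects to allow a comparison of long-term safety, and a count that grows with follow-up is a poor basis for one if follow-up differs between arms.

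**Working it through.** The documents state no event rate, chemotherapy uptake or expected count for this variable, so there is no figure to reproduce. The check is a comparison of the texts, plus arithmetic on window lengths.

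**Step 1. The rules side by side.**

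| Place | Limited to chemotherapy recipients | Limited to the window |
|---|---|---|
| Protocol 2, 3.1, 3.2, 7.2.2, 7.2.3, 7.5, Table 7-1 | yes | yes |
| Protocol 7.5.1.1 | yes | no |
| SAP 6.4.2, description of collection | yes | yes |
| SAP 6.4.2, analysis | no | no |

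**Step 2. Direction of the error.** For chemotherapy given on study, every event inside the window also meets the definition in 7.5.1.1. The wider rule contains the narrower one, so it adds events and loses none.

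**Step 3. What is estimated.** Let C be the number of chemotherapy recipients and N the number in SAF-LTF. Let A be the recipients with an in-window event. Let B be the recipients whose only event is outside the window and is recorded solely because 7.5.1.1 was followed. Let D be everyone else with a recorded event, for example a treatment-related hemorrhage without chemotherapy.

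- Protocol 3.2: A / C.
- SAP 6.4.2, all sites following 7.2.2: (A + D) / N.
- SAP 6.4.2, all sites following 7.5.1.1: (A + B + D) / N.

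Neither SAP quantity equals A / C. The two differ by B / N, which depends on the site's reading, and B can grow with time under observation.

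**Step 4. Scale of the time involved.** Chemotherapy duration is not in the documents, so I assume one course of 3, 6 or 12 months. The window is that duration plus 6 months. Maximum follow-up from last feeder dose is 84 months (prostate) or 60 months (breast), per SAP 5.3.

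| Assumed chemotherapy | Window | Share of 84 months | Share of 60 months |
|---|---|---|---|
| 3 months | 9 months | 9/84 = 11% | 9/60 = 15% |
| 6 months | 12 months | 12/84 = 14% | 12/60 = 20% |
| 12 months | 18 months | 18/84 = 21% | 18/60 = 30% |

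These are shares of the longest possible time, not of events. Observation in 16996 starts at consent, which is later than the last feeder dose, and many subjects will die or leave before the maximum.

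**Step 5. Can the window be rebuilt?** For on-study chemotherapy, yes. Start and stop dates are required by Section 6.1, and AE start and stop dates by Section 7.5.1.3. No section of the SAP plans to combine them.

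**Step 6. Chemotherapy before consent.** If chemotherapy stopped m months before consent, with 0 < m < 6, the last 6 − m months of a six-month tail fall inside 16996; for m = 2 that is 4 months. Section 6.1 does not require that chemotherapy to be entered. SAP 5.2.1 does not list anti-cancer therapy among the feeder data to be integrated, and SAP 5.1 uses only therapy data collected in 16996. Whether a subject treated only before consent belongs to the recipient group is not stated. Chemotherapy still running at consent is received during the study and already falls under 6.1.

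**The case against.** The strongest reply is that 7.5.1.1 only classifies events, while every section that instructs collection carries the window, and that sites are trained and given a telephone script (7.2.2). That sites would follow one clause over the schedule is a possibility, not an observed fact. This stands, and it is why the claim is that the percentage *can* depend on the reading, not that it does.

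Second, the window disappears from the result mainly because the sponsor chose a simplified analysis and declared it. This also stands. A reader might infer that the clause in 7.5.1.1 is what spoils the variable; with a windowed analysis its effect would be removed. But declaring the simplification discloses only that chemotherapy association is ignored. It does not deal with events being collected under two rules, and correcting the clause alone would leave the result unwindowed.

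Third, a reader might infer that windows already open at consent are missed. The documents do not show this. Table 7-1 footnote c asks for any cancer treatment without the limit in 6.1, feeder databases may hold the dates, and a missing chemotherapy record cannot remove an event from a count that ignores chemotherapy. What remains is an unstated rule.

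Fourth, a reader might put a constant hemorrhage rate on the wider period and project a several-fold excess over seven years. The documents give no rate, the rate outside chemotherapy need not equal the rate inside, and Section 1.1 describes a very limited life expectancy in metastatic castration-resistant disease. Such a projection ignores death and is not supported.

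Finally, the study is descriptive, with no formal testing. That limits the consequence to interpretation, but this is one of the stated primary variables.

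**Conclusion.** The point holds as an inconsistency with a consequence for interpretation. The AE definition lacks the window that the rest of the protocol applies. For on-study chemotherapy this over-collects and loses nothing, and the SAP then reports all collected events over all SAF-LTF participants. As written, the plan does not deliver the incidence defined in Section 3.2, and differences between sites or in follow-up length could enter the reported percentage unseen.

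The number of extra events cannot be derived. The available scale is a window of 9 to 18 months against at most 84 or 60 months, assuming a single course of 3 to 12 months. The number of subjects with chemotherapy stopped shortly before consent cannot be derived either, and for them the finding is an ambiguity to settle, not a demonstrated loss.

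**What to change.** 1. In Protocol 7.5.1.1, add "during chemotherapy treatment and for up to 6 months thereafter" to the febrile neutropenia and hemorrhage clause, so that it agrees with 7.2.2 and Table 7-1. At the same time reconcile 7.5.1.2.3, which confines collection to related events and excepts malignancies and bone events but not these.
2. In SAP 6.4.2, use recorded chemotherapy start and stop dates and AE start dates to flag each event as inside or outside the window. Add an undetermined category for incomplete dates, because the rule in Appendix 8.1 moves a missing AE start date to the consent date and could change the flag.
3. Report the in-window incidence among chemotherapy recipients beside the simplified all-participant summary.
4. State whether chemotherapy that stopped within six months before 16996 consent opens a window. If it does, take its stop date from feeder records where available.

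The second and third items matter most. The protocol version dates from 2018 and the SAP from 2024, so rewording the definition will not change data already collected, whereas the flag works on them. The cost is one clause, one derived variable and one extra table, possibly a small data query, and fewer events counted in the windowed result.

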### **Definition of serious adverse event**

An SAE is classified as any untoward medical occurrence that, at any dose, meets any of the following criteria (a - g):

- a. Results in death
- b. Is life-threatening

The term ‘life-threatening’ in the definition refers to an event in which the subject was at risk of death at the time of the event, it does not refer to an event which hypothetically might have caused death if it were more severe.

- c. Requires inpatient hospitalization or prolongation of existing hospitalization

A hospitalization or prolongation of hospitalization will not be regarded as an SAE if at least one of the following exceptions is met:

- The admission results in a hospital stay of less than 12 hours
- The admission is pre-planned (e.g., elective or scheduled surgery arranged prior to the start of the study; admission is part of the study procedures as described in Section 7.2).
- The admission is not associated with an AE (e.g., social hospitalization for purposes of respite care)

However, it should be noted that invasive treatment during any hospitalization may fulfill the criterion of ‘medically important’ and as such may be reportable as an SAE dependent on clinical judgment. In addition, where local regulatory authorities specifically require a more stringent definition, the local regulation takes precedence.

- d. Results in persistent or significant disability / incapacity

Disability means a substantial disruption of a person's ability to conduct normal life's functions.

- e. Is a congenital anomaly / birth defect
- f. Is another serious or important medical event as judged by the investigator
- g. Is an occurrence of leukemia, myelodysplastic syndrome, aplastic anemia, and primary bone cancer or any other new primary malignancy (regardless of the investigator's causality assessment)

If disease progression leads to signs and symptoms that meet the criteria for seriousness (e.g., hospitalization), the associated signs and symptoms should be reported as SAEs, not the underlying cause (i.e., "progressive disease" should not be recorded as an SAE). In this case disease progression should be mentioned on the SAE form as an "alternative explanation."

An isolated laboratory abnormality that meets the criteria for National Cancer Institute (NCI)-Common Terminology Criteria for Adverse Events (CTCAE) Grade 4 classification is not reportable as an SAE, unless the investigator assesses that the event meets standard International Conference of Harmonisation criteria for an SAE. All laboratory abnormalities, including CTCAE Grade 4 abnormalities, will be documented on the laboratory eCRF (including values reported from central laboratories).

